2. PROTOCOL SUMMARY

2.1 Study Number and Title

SPY LNM 01 (FILM-B): A Single Arm, Prospective, Open Label, Multicenter Study Assessing the Safety and Effectiveness of IC2000 and SPY Fluorescence Imaging Systems in the Visualization of Lymphatic Vessels and Lymph Nodes during Lymphatic Mapping and Sentinel Lymph Node Biopsy in Subjects with Breast Cancer

Clinical Phase: Phase III - Investigational Device Study

2.2 Study Objectives

Primary

 To assess the effectiveness of IC2000 and SPY-PHI (SPY Portable Handheld Imager; also called "IC2000 and SPY") Fluorescence Imaging System in the identification of lymph nodes (histology confirmed lymph nodes), during lymphatic mapping and sentinel lymph node biopsy in subjects with early stage breast cancer.

Secondary

- To evaluate the effectiveness of IC2000/SPY and Tc99m/Gamma Probe in the identification of at least one lymph node (histology confirmed lymph node) per subject.
- To evaluate the effectiveness of IC2000 and SPY as an intraoperative fluorescence visualization tool in delineation and mapping of lymphatic vessels in the identification of lymph nodes (histology confirmed lymph nodes).
- To confirm the safety of intradermal injection of IC2000 in intraoperative delineation and mapping lymphatic vessels and identification of lymph nodes.

2.3 Study Design

This is a prospective, open label, multicenter, non-inferiority within-patient study to determine the effectiveness of IC2000 (Indocyanine Green (ICG) for Injection) and the SPY Portable Handheld Imaging System (SPY-PHI) as an intraoperative fluorescence visualization tool, in the visual identification of lymphatic vessels and lymph nodes (LNs) during lymphatic mapping and sentinel lymph node biopsy (SLNB) procedures as confirmed by Technitium99m (Tc99m) and Gamma Probe. Enrollment will not exceed 1 centers in North America. Prior to enrolling study subjects, participating surgeons at each center will be:

- Required to have completed a minimum of (5) lymphatic mapping and sentinel lymph node identification procedures using SPY-PHI with ICG.
 - Trained to perform the intradermal injection technique with ICG.

Screening

Subjects diagnosed with breast cancer with either Ductal Carcinoma in Situ (DCIS) (Stage 0, T_{is}, N0, M0) or clinical stage IA, IB or IIA¹ who are scheduled for surgery that includes clinically indicated SLNB with Tc-99m radioactive colloid and Gamma Probe will be included to determine if they meet the inclusion/exclusion criteria (Note: Only subjects who subsequently consent to undergo LN mapping and identification using IC2000 and SPY-PHI as an intraoperative fluorescence visualization tool may be enrolled in the study – see below for details).

Subjects will be evaluated at baseline to determine if they meet the inclusion/exclusion criteria of the FILM-B protocol. Subjects considered for inclusion in the study will be assessed to determine overall health status including demographics, vital signs, diagnosis and relevant medical history/underlying conditions.

Day 0

As per standard of care, all subjects will receive an injection of Tc-99m radioactive colloid either the day before or the morning of surgery. On the day of surgery subjects will receive an injection of IC2000 at the start of surgery while the subject is in the operating room and under anesthesia. The injection will occur prior to SLNB as IC2000 and SPY will be used to map and identify LNs for excision.

The breast(s) identified with DCIS or stage IA, IB or IIA cancer will be injected with IC2000 (2.5 mg/ml solution) in the peri-areolar area as described below.

Visual Identification, Mapping Procedure and LN Excision:

Following the intradermal peri-areolar injection of IC2000, the surgeon will intraoperatively map the lymphatic vessels from the injection site in order to identify the LNs based on intraoperative fluorescence visualization using IC2000 and SPY-PHI. #maging will commence by tracing the lymphatic vessels from the point of

Clinically suspicious LNs designated as palpable masses will be excised regardless of visible fluorescence or if deemed 'hot' with a gamma probe.

Classification of LNs:

All LNs identified by IC2000/SPY-PHI and Tc99m/Gamma Probe will be classified *exvivo or in-vivo* by the surgical investigator:

- Fluorescent only
- 2. Tc99m only
- 3. Both (Fluorescent and Tc99m positive)
- 4. Clinically suspicious (Fluorescence and Tc99 negative)

Failed mapping is defined as no LNs detected either by Tc99m and Gamma Probe, IC2000 and SPY or LNs deemed clinically suspicious.

Details of the surgery, including intraoperative findings will be documented. Surgical data will be documented on study specific case report forms (CRFs).

Follow-up and Post-Operative Complications

Subjects will have standard of care assessments throughout the study according to the hospital / institution's standard procedures. Subjects will be monitored for the occurrence of any adverse events/adverse device effects on the date of discharge and on Day 30 (±7 days).

2.4 Study Population

To be eligible for the study, subjects must meet the following main inclusion criteria:

- 18 years of age or older.
- Subjects with American Cancer Society Clinical Stage 0 Ductal Carcinoma in Situ (DCIS) (Stage 0, T_{is}, N0, M0), IA (T1*, N0, M0), IB ((T0, N1mi, M0) or T1*, N1mi, M0)) or Stage IIA (T0, N1**M0, or T1, N1**, M0 or T2, N0, M0)¹ breast cancer undergoing surgery to remove tumor draining LNs.

Where:

- o T_{is} = Ductal carcinoma in situ
- T0 = No evidence of primary tumor
- o T1 = Tumor ≤ 20 mm in greatest diameter
- T1* = Includes T1mi
- o T2 = Tumor >20 mm but ≤ 50 mm in greatest diameter
- N0 = No regional lymph node metastasisq1`
- N1 = Metastasis to movable ipsilateral level I, II axillary LNs
- N1** = T0 and T1 tumors with nodal micro-metastasis only are excluded from Stage IIA and are classified Stage IB.
- o mi = Micro-metastasis
- M0 = Disease has not metastasized
- Subjects with clinically negative nodal status (N0) with or without neoadjuvant therapy.
- Subjects with negative metastatic involvement (M0).
- Subjects of child-bearing potential must not be pregnant or lactating and must have a negative pregnancy test at Baseline.
- Have signed an approved informed consent form for the study.
- Be willing to comply with the protocol.

Subjects meeting any of the following criteria will be excluded from the study:

- Have had prior axillary surgery or ipsilateral radiation in the breast(s) that is planned for this procedure.
- Advanced breast cancer subjects with stage IIB, III or IV.
- Known allergy or history of adverse reaction to ICG, iodine or iodine dyes.
- Subjects who have participated in another investigational study within 30 days prior to surgery.
- Pregnant or lactating subjects.

Subjects who, in the Investigator's opinion, have any medical condition that
may make the subject a poor candidate for the investigational procedure, or
interferes with the interpretation of study results.

2.5 Study Devices and Imaging Agents

In this study, IC2000 and SPY-PHI will be assessed as an intraoperative fluorescence visualization tool in the identification of LNs during lymphatic mapping in subjects undergoing sentinel lymph node biopsy with early stage breast cancer.

SPY-PHI is intended for intraoperative visual assessment of blood vessels and related tissue perfusion by surgeons. It is an imaging system used in capturing and viewing fluorescent images for visual assessment of blood flow, as an adjunctive method for the evaluation of tissue perfusion, and related tissue-transfer circulation in tissue and free flaps during various surgical procedures.

SPY-PHI allows for real time, intraoperative visualization and video of near infrared (NIR) fluorescence, which are acquired by using the imaging agent.

The imaging agent used with SPY-PHI is Indocyanine Green (IC2000), which is a sterile, water-soluble tricarbocyanine dye with a peak spectral absorption at 800-810 nm in blood plasma or blood. IC2000 contains not more than 5.0% sodium iodide. In this study, investigational ICG, IC2000, will be administered to subjects through an intradermal injection into the peri-areolar area of the breast.

Tc-99m radioactive colloid injection is a clear, colorless aqueous solution and will be injected into the peri-areolar area of the breast as per standard of care.

Tc99m will be used in conjunction with the Gamma Probe. Gamma Probes detect the presence of gamma rays emitted from radioactive isotopes in body organs or tissue. The system provides an increasing or decreasing sound and visual indicator (Count Bar) that vary in pitch as level of gamma radioactivity increases or decreases³.

2.6 Study Variables

Primary Variable

- To assess the effectiveness of IC2000 and SPY-PHI (SPY Portable Handheld Imager; also called "IC2000 and SPY") Fluorescence Imaging System in the identification of lymph nodes (histology confirmed lymph nodes), during lymphatic mapping and sentinel lymph node biopsy in subjects with early stage breast cancer.
 - Defined as the proportion of lymph nodes identified and excised by IC2000/SPY compared to the proportion of lymph nodes identified and excised by Tc99m/Gamma Probe, (histology confirmed lymph nodes). Denominator is the total number of lymph nodes identified and excised, inclusive of clinically suspicious lymph nodes (histology confirmed).

Secondary Variables

- To evaluate the effectiveness of IC2000/SPY and Tc99m/Gamma Probe in the identification of at least one lymph node (histology confirmed lymph node) per subject.
 - Defined as the proportion of subjects in which at least one lymph node is identified by IC2000/SPY, and Tc99m/Gamma Probe, (histology confirmed lymph nodes). Numerator is the number of subjects who have at least one lymph node identified by IC2000/SPY, and the number of subjects who have at least one lymph node identified by Tc99/Gamma Probe, respectively (histology confirmed). Denominator is the total number of subjects where mapping was attempted.
- To evaluate the effectiveness of IC2000 and SPY as an intraoperative fluorescence visualization tool in delineation and mapping of lymphatic vessels in the identification of lymph nodes (histology confirmed lymph nodes).
 - Defined as the proportion of lymph nodes identified by IC2000 and SPY (histology confirmed lymph nodes) by following a fluorescent lymphatic vessel compared to the proportion of lymph nodes identified by IC2000 and SPY (histology confirmed lymph nodes) with no lymphatic vessels visible by IC2000 and SPY. Denominator is the total number of lymph nodes identified by any method (histology confirmed).
- To confirm the safety of intradermal injection of IC2000 in intraoperative delineation and mapping lymphatic vessels and identification of lymph nodes.
 - Defined by the incidence of adverse events with IC2000.

2.7 Study Procedures and Assessments

The following assessments and procedures will be performed:

- Vital signs, height, weight, demographics, surgical predictive factors.
- Relevant medical history and underlying conditions.
- Assessment of eligibility criteria.
- Tc-99m radioactive colloid administration.
- Imaging agent (IC2000) administration.
- Mapping of lymphatic vessels using IC2000 and SPY-PHI.
- Identification of lymph nodes using IC2000 and SPY-PHI
- Excision of lymph nodes identified with IC2000 and SPY-PHI
- Confirmation and/or identification of lymph nodes with Tc-99m radioactive colloid and Gamma Probe ex-vivo and in-vivo.
 - LNs identified *in-vivo* by Tc99 and Gamma Probe will be excised under visual guidance of IC2000 and SPY.

- Clinically suspicious LNs designated as palpable masses will be excised.
- Failed mapping will be documented.
- Documentation of lymphatic mapping and SLNB procedure.
- Classification of excised lymph nodes.
- Histological assessment of all excised lymph nodes.
- Concomitant medications.
- Assessment of surgical complications.
- Adverse events and adverse device effects.
 - Follow-up visits will occur on the date of discharge, and Day 30. Subjects with a discharge date later than Day 30 will have their last study visit on Day 30.

2.8 Sample Size and Statistical Analysis

This is a prospective, open label, multicenter, non-inferiority within-patient study to determine the effectiveness of IC2000 (Indocyanine Green (ICG) for Injection) and the SPY Portable Handheld Imaging System (SPY-PHI) as an intraoperative fluorescence visualization tool, in the visual identification of lymphatic vessels and LNs including LNs during lymphatic mapping and SLNB procedures as confirmed by Tc99m and Gamma Probe. A sample size of 356 LNs contributed by approximately 137 evaluable patients will be required using the following assumptions:

- 1. The average detection rate with Tc99m and Gamma Probe will be 91.6%.
- The average detection rate with IC2000 and SPY will be 96%.
- A power of 90%.
- 4. A non-inferiority margin of 5 percentile units.
- An average of 2 LNs is expected to be excised per patient.

Estimating that 6% of patients will be excluded from the per-protocol (PP) population (see section 14.1), approximately 379 LNs are required.

Additional details are included in Section 14.7, Sample Size Considerations.

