7. INVESTIGATIONAL PLAN

7.1 Study Design Overview

This is a prospective, open label, multicenter, non-inferiority within-patient study to determine the effectiveness of IC2000 (Indocyanine Green (ICG) for Injection) and the SPY Portable Handheld Imaging System (SPY-PHI), as an intraoperative fluorescence visualization tool in the visual identification of lymphatic vessels and identification of LNs during lymphatic mapping and SLNB procedures as confirmed by Tc99m and Gamma

Probe. Enrollment will not exceed 190 subjects at up to 10 centers in North America. Prior to enrolling study subjects, participating surgeons at each center will be:

- Required to have completed a minimum of (5) lymphatic mapping and sentinel lymph node identification procedures using SPY-PHI with ICG.
- Trained to perform the intradermal injection technique using ICG.

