14.7 Handling of Missing Data

14.8 Sample Size Considerations

This is a single arm, non-inferior, sequential design, paired comparison study of IC2000 and SPY with the standard of care, Tc99m/Gamma Probe in the identification of lymph nodes during lymphatic mapping and sentinel lymph node biopsy. The sample size calculation for the primary endpoint was performed using nQuery Advisor® 7.0 (Copyright® 1995-2007, Statistical Solutions Ltd). To support the sample size calculation, the average LN detection rate with IC2000 and SPY (Q_T) of 96% was assumed, based on the recent meta-analyses; Mok et al. 56 An average detection rate of 91.6% has been assumed for Tc99m and Gamma Probe (Q_C) 57 A 5% non-inferiority margin is deemed to be conservative for sentinel lymph node biopsy (SLNB).

Assuming an average of 2 excised LNs per patient evaluated by both methodologies with 11.2% discordance $\frac{57}{1}$, 137 subjects would be required to prove the non-inferiority of IC2000 and SPY with a non-inferiority margin of 5% using a one-sided 2.5% alpha and 90% power. A 1.0% Q_T advantage would establish non-inferiority.

Lower one-sided 97.5% confidence bound: Difference in paired proportions (simulation)

	90% Power	1-sided p=0.025
Confidence level, 1-α (one-sided)	0.975	0.975
Expected difference, $Q_T - Q_C$, Δ	0.044	0.01
Proportion discordant, $d = q_{10} + q_{01}$	0.112	0.112
Proportion both yes, q ₁₁	0.883	0.883
Lower limit for Q _T - Q _C , LL	-0.050	-0.050
Number of simulations	1000	1000
Random seed for simulations	123	123
Power (%)	90	NA
n (number of paired evaluations)	137	137

Based on a 2-level hierarchical model in which nodes are nested within subjects, and given that we expect an average of 2 nodes to be excised per patient the aforementioned sample size needs to be multiplied by an inflation factor (IF), aka Design Effect (DEFF $\frac{54,55}{}$), of 1+(n-1)*ICC where n is the average sample size per cluster and ICC (expected to be at most 0.1) is the intra-class correlation: IF = 1+ (2x2 – 1) x 0.1 = 1.3, where n was multiplied by 2 due to the fact that LNs will be identified using 2 different methods. Based on a total of 274 LNs and an IF of 1.3, a sample size of 356 lymph nodes will be required. Estimating that 6% of patients will be excluded from the per-protocol (PP) population (see Section 14.1), approximately 379 LNs are required.

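### Section 2.8 pairs 356 lymph nodes with about 137 evaluable patients, but at the assumed 2 nodes each, 356 nodes need 178 patients and 137 patients give 274 nodes.

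*Combined protocol and SAP*

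**What the plan says.** Section 2.8 gives the required size in both nodes and patients: "A sample size of 356 LNs contributed by approximately 137 evaluable patients will be required using the following assumptions". The list under that sentence includes "An average of 2 LNs is expected to be excised per patient". The section then allows for 6% of patients falling outside the per-protocol population and arrives at about 379 nodes.

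Section 14.8 gives the derivation. It starts from "Assuming an average of 2 excised LNs per patient evaluated by both methodologies with 11.2% discordance" and obtains 137 subjects "using a one-sided 2.5% alpha and 90% power". It computes an inflation factor (IF) of 1.3 for nodes nested within subjects and applies it to the node count: "Based on a total of 274 LNs and an IF of 1.3, a sample size of 356 lymph nodes will be required". The 6% allowance then gives 379 nodes. No patient number is stated after the inflation.

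Section 7.1 sets the ceiling: "Enrollment will not exceed 190 subjects at up to 10 centers in North America".

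**The concern.** The sentence in Section 2.8 appears to join two stages of one calculation: a patient count from before the clustering inflation and a node count from after it.

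This matters because the per-protocol population is primary (Section 14.1), so the number of evaluable patients is what tells the study team that accrual is sufficient. If accrual is managed to 137 evaluable patients, the node requirement is missed. If it is managed to 356 nodes, the patient figure in the synopsis understates what sites, ethics committees and the DSMB should expect. A reader who checks the synopsis against Section 14.8 finds 137 there as well, apparently confirmed, because 14.8 never gives the inflated patient number. The cross-reference does not help either: Section 2.8 points to 14.7 for sample size, but 14.7 is headed as missing-data handling and the sample size is in 14.8.

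**Working it through.** **Inputs**

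- Section 2.8: 356 nodes, about 137 evaluable patients, 2 nodes per patient.
- Section 14.8: 137 subjects, 274 nodes, inflation factor 1.3, expected difference 0.044, discordance 0.112, margin 0.05, one-sided alpha 0.025, power 90%.
- Sections 2.8 and 14.8: 6% excluded from the per-protocol population, 379 nodes.
- Section 7.1: at most 190 subjects.

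**1. The base figure of 137.** For a paired non-inferiority comparison, n = (z_α + z_β)² × variance / (difference + margin)².

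- With variance 0.112 − 0.044² = 0.1101: n = (1.960 + 1.282)² × 0.1101 / 0.094² = 131.
- With variance 0.112: n = 134.
- At n = 137, the normal approximation gives 91.3% power. Simulation gives 90.2% with a score test, 92.6% with a Wald interval and 88.1% with a continuity-corrected Wald interval.

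The plan's 137 came from a simulation option in its software and is consistent with these results.

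**2. The plan's chain from 137 to 379.**

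- 137 × 2 = 274 nodes.
- 274 × 1.3 = 356.2, stated as 356.
- 356 / 0.94 = 378.7, stated as 379.

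Every link reproduces.

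**3. The pairing in Section 2.8.**

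- 137 patients × 2 = 274 nodes, not 356. The shortfall is 356 − 274 = 82 nodes, and 82 / 356 = 23%.
- 356 nodes / 2 = 178 patients, not 137. The gap is 178 − 137 = 41 patients, and 41 / 137 = 30%.
- 356 / 137 = 2.60 nodes per patient, against the assumed 2.

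**4. Which patient count fits the rest of the plan.**

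| | 137 evaluable | 178 evaluable |
|---|---|---|
| Nodes at 2 per patient | 274 | 356 |
| Enrolled, allowing 6% exclusion | 137 / 0.94 = 145.7, about 146 | 178 / 0.94 = 189.4, about 190 |
| Agrees with the 190 cap | no | yes |

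Three further checks point to 178: 137 × 1.3 = 178.1; 379 / 2 = 189.5; 190 × 0.94 = 178.6.

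**5. The other reading of 137.** The table in Section 14.8 labels 137 as the number of paired evaluations, which could mean nodes and not subjects. In that case 137 × 1.3 = 178 nodes, from about 178 / 2 = 89 patients. This does not give 356 nodes from 137 patients either.

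**The case against.** The strongest reply is that the error has little effect. The hypothesis and analysis are at node level, the node targets of 356 and 379 agree between Sections 2.8 and 14.8, and the legible enrolment limit of 190 already fits them. No legible text stops accrual at 137 patients. All of this stands: it limits the consequence but leaves the sentence wrong.

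A second reply is that a 274-node trial might still have ample power. If 137 means node pairs, then 274 / 1.3 = 211 effective pairs, the standard error is √(0.1101 / 211) = 0.0228, and 0.094 / 0.0228 − 1.96 = 2.16, or about 98% power. That is a fair caution against reading the 23% shortfall as lost power, and no loss of power is claimed here. But the reassurance depends on the table's label for 137. It does not follow if 137 means subjects, as the text of Section 14.8 has it.

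Third, 178 is only the figure that matches the existing chain; it is not proven to be the size the trial needs. That is correct, so the replacement is conditional on the chain being kept.

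Finally, the word approximately in Section 2.8 cannot absorb a 30% difference. The figure in Section 8.1 is not legible in the public copy, so nothing is inferred from it.

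**Conclusion.** The concern holds. Section 2.8 states three figures that cannot all be true, and Section 14.8 shows that the patient count was left at its pre-inflation value. On the plan's own assumptions (2 nodes per patient, inflation 1.3, 6% exclusion), 356 nodes correspond to 178 evaluable and about 190 enrolled patients.

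This is a wrong stated sample size in the main sample-size sentence, so it is more than a typing slip and should be corrected. It does not show that enrolment is under-planned, because the cap of 190 already agrees with 178. Nor does it settle whether the unit of 137 in Section 14.8 is subjects or node pairs.

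**What to change.** First confirm what the 137 in Section 14.8 counts. If the 356/379 node chain is kept, change the patient count in Section 2.8 to about 178 evaluable patients (about 190 enrolled), and add the inflated patient number to Section 14.8, for example as 137 × 1.3 = 178 evaluable and 178 / 0.94 = about 190 enrolled. If the chain is revised, use the matching pair of node and patient numbers instead.

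In either case, state the same pair in Sections 2.8 and 14.8 and check that Sections 7.1 and 8.1 agree with it. Correct the cross-reference in 2.8 from 14.7 to 14.8 at the same time.

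The cost is one number in the synopsis and a sentence in 14.8. If the chain is kept, the margin, the analysis and the enrolment cap stay as they are.

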4. ABBREVIATIONS AND DEFINITIONS

ADE Adverse Device Effect

AE Adverse Event

ALND Axillary Lymph Node Dissection
ASBrS American Society of Breast Surgeons

AT As-treated BD Blue Dyes

CFR Code of Federal Regulations

CRF Case Report Form
DCIS Ductal Carcinoma In-Situ

DSMB Data and Safety Monitoring Board

EC Ethics Committee

FDA Food and Drug Administration

GCP Good Clinical Practice

GMP Good Manufacturing Practice

H&E Hematoxylin and Eosin

HD High Definition

HSA Human Serum Albumin

IA Imaging Agent
IB Isosulfane Blue

ICH International Conference on Harmonization

ICG Indocyanine Green

IRB Institutional Review Board

LN Lymph Node MB Methylene Blue

mITT Modified Intent-to-treat

NIR Near-Infrared

SADE Serious Adverse Device Effect

SAE Serious Adverse Event SLN Sentinel Lymph Node

SLNB Sentinel Lymph Node Biopsy

SPY SPY Fluorescence Imaging Systems

SPY-PHI Open Field Handheld Fluorescence Imaging System

Tc99m Technetium 99m

Tc99m – TM Technetium 99m – Tilmanocept Tc99m – SC Technetium 99m – Sulfur Colloid

US United States

UADE Unanticipated Adverse Device Effect

VIS Visible

